### Dose reductions and modifications

Memorial Sloan Kettering Cancer Center  
[name]  
[name]

This study will use the NCI Common Toxicity Criteria (CTC) AE version 5.0 for toxicity assessment.

### Alpelisib

The recommended dose modifications for adverse reactions (ARs) are listed in Table 1.

Table 1. Alpelisib dose reduction guidelines

Alpelisib dose level	Dose and schedule	Number and strength of tablets
Starting dose	300 mg once daily	Two 150 mg tablets OR ALTERNATIVELY One 200mg and two 50mg tablets can be used to reach the 300 mg dose level
First dose-reduction	250 mg once daily	One 200 mg tablet and one 50 mg tablet
Second dose-reduction	200 mg once daily 	One 200 mg table

If further dose reduction below 200 mg once daily is required, discontinue alpelisib

### Rash

Table 2. Dose modification and management for rash.

Grade	Recommendation
Grade 1  Macules/papules covering <10% BSA with or without symptoms (e.g., pruritus, burning, tightness)	No dose adjustment required.  OTC moisturizers and sun protection
Grade 2  Macules/papules covering 10 - 30% BSA with or without symptoms (e.g., pruritus, burning, tightness); limiting instrumental ADL; rash covering > 30% BSA with or without mild symptoms	No dose adjustment required.  OTC moisturizers and sun protection
Grade 3 Macules/papules covering >30% BSA with moderate or severe symptoms; limiting self care ADL	Interrupt alpelisib.  Prednisone 50mg a day over 10 days (with pneumocystis prophylaxis and PPI). Restart alpelisib as per package insert.
Grade 4 (SJS/TEN)  Life-threatening consequences; urgent intervention indicated	Permanently discontinue alpelisib, consult with dermatologist

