## 1.0 PROTOCOL SUMMARY AND/OR SCHEMA

This is a multi-center, open-label, phase 2 trial testing the efficacy and safety of 2 interventions that target rash during PI3K inhibitor therapy in postmenopausal women and men with histologically-confirmed, hormone receptor (HR)-positive, HER2-negative, PIK3CA mutant metastatic breast cancer (MBC). A total of 63 patients will be enrolled into one arm: benralizumab 30mg in combination with standard of care (SOC) endocrine therapy (fulvestrant or AIs or aromatase inhibitors (AIs)) and PI3K inhibition (alpelisib). A total of 43 patients will be enrolled at MSKCC and a total of 20 patients will be enrolled at the participating external institutions (10 patients at Stanford University and 10 patients at Dana Farber Cancer Institute). The primary endpoint is the proportion of patients with grade  $\leq 1$  rash rate at 4 weeks.

**Patient Population:** The primary study population will be postmenopausal women and men with histologically-confirmed, HR-positive, HER2-negative, *PIK3CA* mutant MBC who have received no more than 2 lines of endocrine-based therapy in the metastatic setting.

**Design:** A multi-center, open-label, phase 2 trial testing the efficacy and safety of one interventions (one anti IL-5 receptor antibody and one antihistamine) that target the maculopapular rash during PI3K inhibitor therapy in patients with HR-positive, HER2-negative, *PIK3CA* mutant MBC receiving first or second line therapy. Study participants (n=112) will enrolled to one arm: benralizumab (anti-IL5ra) in combination with SOC endocrine therapy (fulvestrant or AIs) and PI3K inhibition (alpelisib). The primary endpoint is the grade  $\leq 1$  rash rate at 4 weeks. The study size is determined to compare the grade  $\leq 1$  rash rate at four weeks with historical controls. It has been reported that approximately 34% of patients receiving alpelisib will develop  $\geq$  grade 2 rash within the first 30 days. The corollary is that 66% of historical controls will have grade  $\leq 1$  rash within the first 30 days. An increase in rash control to approximately 88% is deemed to be clinically meaningful with the investigational agent under investigation (IL5r antibody). A sample size of 57 patients per group will achieve an 80% power to detect an odds ratio of 4.0 with respect to the primary endpoint. The proportion in the experimental group is assumed to be 0.66 under the null

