hypothesis and 0.88 under the alternative hypothesis. The proportion is 0.66. If it is assumed that 10% of patients will withdraw consent or be lost to follow up, then 63 patients will need to be enrolled into this trial.

**Treatment Plan:** All participants will receive SOC endocrine therapy (fulvestrant or AIs) and PI3K inhibition (alpelisib). Participants will receive benralizumab 30mg subcutaneously on day -1. All participants will be monitored at regular visits for the duration of the trial. After 4 weeks, patients will be followed for safety at 90 days and disease progression for 1 year.

**Estimated Time to Completion:** 1 years.

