### Secondary Objectives

1. To determine the effect of prophylactic anti-IL-5 receptor inhibition on alpelisib dose interruption or modification when compared to historical controls as determined by relative dose intensity (RDI) during the initial 4 weeks of therapy (4W-RDI).
2. To determine the effect of prophylactic anti-IL-5 receptor inhibition on quality of life when compared to historical controls using the Functional Assessment of Cancer Therapy–Breast (FACT-B) and the PRO-CTCAE.
3. To determine the effect of prophylactic anti-IL-5 receptor inhibition on cumulative steroid dose when compared to historical controls.
4. To determine the effect of prophylactic anti-IL-5 receptor inhibition on time to development of alpelisib grade  $\geq 2$  rash when compared to historical controls.
5. To determine the safety of anti-IL-5 receptor inhibition and historical controls in patients receiving alpelisib, defined as adverse events definitely, possibly or probably related to anti-IL-5 receptor inhibition or historical controls.
6. To determine the effect of anti-IL-5 receptor and historical controls on non-skin alpelisib-related adverse events (eg. nausea, diarrhea, vomiting, anorexia, fatigue, weight loss).
7. To determine the overall response rate (ORR) and progression free survival (PFS) at 6 and 12 months post treatment initiation.

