### 3.5. Eosinophils and Drug Reactions

In areas where helminth exposure is uncommon, medication-related drug reactions are a common cause of peripheral and blood eosinophilia (Ramirez and Frias, British Pharmacol Soc 2017). In the absence of systemic involvement, this condition generally constitutes a drug effect that can be caused by a myriad of medication classes, such as penicillin and sulphonamide drugs, and resolves upon drug discontinuation (Khoury and Bochner, JACIP 2018). In the oncology setting, eosinophil-related cutaneous adverse events (ercAEs) are also frequent (10-20%) (Fujisawa et al, J Dermatol Sci 2017), but their impact is greater: they result in interruption or discontinuation of life-prolonging antineoplastic agents, negatively affect a patient's quality of life, may affect other organs (i.e. liver and kidneys as part of the Drug Rash with Eosinophilia and Systemic Symptoms (Cho et al, Int J Mol Sci 2017)), and usually require treatment with corticosteroids which carry their own set of toxicities (i.e. hyperglycemia). There are no FDA approved therapies for drug reactions associated with eosinophils, and drug interruption/discontinuation and systemic steroids are current reactive management strategies.

Abundant clinical data suggests that eosinophils play a pivotal role in cancer and cutaneous reactions to anticancer therapies (Davis and Rothenberg, Cancer Immunol Res 2014; Tracey et al, Am J Dermatopathol 2017; Sakkal and Miller, Curr Med Chem 2016; Roufousse 2015; Blank et al, Eur J Pharmacol 2016)). Indeed, between 1/1/2015 and 3/11/2019 there were 2652 patients evaluated by the dermatology service at MSKCC with skin conditions and associated eosinophilia ([name], unpublished data). Of these, 584 patients were receiving immunotherapies, and the remaining were receiving other drugs including cytotoxic chemotherapy, targeted therapies, or supportive care drugs. Therefore, eosinophils

represent an attractive target for the treatment of dermatologic adverse events (dAEs), as they have been reported in biopsy samples from skin, gut, and lungs in patients treated with immune checkpoint inhibitors (CPIs) developing rash, colitis, and pneumonitis in the majority of patients with drug reactions (Kizawa et al, J Clin Oncol 2019; Occhipinti et al, Drug Saf Case 2018; Furubayashi et al, Mol Clin Oncol. 2019; Georgianos et al, Case Rep Nephrol 2019).

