## 14.0 BIOSTATISTICS

### Sample Size

This will be a single arm trial. The target sample size is intended to test the hypothesis that benralizumab reduces the frequency of grade  $\geq$  grade 2 rash at 4 weeks relative to the historical controls in patients receiving alpelisib. The primary endpoint in the current study will be the proportion of patients to achieve a rash grade of 1 or less. It has been reported that approximately 34% of patients receiving alpelisib will develop  $\geq$  grade 2 rash within the first 30 days. An increase in rash control to approximately 88% is deemed to be clinically meaningful with the investigational agent. Sample sizes of 57 patients achieves an 80% power to detect a difference based on a two sample proportions test. Due to potential attrition during the course of the study, the sample size will be increased by 10%. The resultant sample size will be 63 patients.

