the Benralizumab group over the study period will be compared using the Wilcoxon Rank Sum test. Time to the development of grade 1 or 2 rash will be evaluated using Kaplan-Meier time to event curves and assessed using the log rank test and Cox proportional hazards regression analysis. The Yates corrected chi square test will be used to compare the frequency of non-skin alpelisib related adverse events between groups, as well as 6 and 12 month ORR and PFS. Differences between the Benralizumab group on IL-5 inhibition and antihistamines and non-skin alpelisib related adverse events will be evaluated using linear mixed models. Changes in inflammatory biomarkers in skin and related to rash and all other exploratory endpoints will only be evaluated graphically with descriptive statistics. Given the exploratory nature of the current trial, there will be no adjustments for multiplicity. All the statistical analyses will be performed using SAS® Version 9.4 or higher. De-identified data will be shared via MSK secured e-mail quarterly to Augmentium Pharma Consulting for statistical analysis.

Patients may be removed from the study for various reasons as outlined in section 12.0 of the protocol. Descriptive statistics will be reported separately for patients removed from the study, including a summary of reasons for removal, their median duration in the study and range, median, range, and the distribution of rash grades at all follow-up times prior to their removal from the study.

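### Steroid dose and alpelisib dose changes are compared with historical controls whose rash care is not described, so a difference in management could be read as a benralizumab effect

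*Combined protocol and SAP*

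**What the plan says.** The trial has a single arm (Section 14, Sample Size). Secondary objective 3 in Section 2.0 is "To determine the effect of prophylactic anti-IL-5 receptor inhibition on cumulative steroid dose when compared to historical controls". Objective 1 makes the same kind of comparison for alpelisib interruption or modification, measured by four-week relative dose intensity (RDI). Section 14 (General Statistical Plan) says that steroid dose "will be compared using the Wilcoxon Rank Sum test" and that the number of dose reductions and delays will be compared by Poisson regression. The Wilcoxon sentence names only the benralizumab group. Section 13.2 measures steroid use as total systemic corticosteroid in mg.

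Rash care in the trial is set out by grade in Section 10, Table 2, in a column headed as a recommendation. Grade 2 includes "limiting instrumental ADL; rash covering > 30% BSA with or without mild symptoms"; no dose adjustment is required, and only moisturizer and sun protection are listed. At grade 3, alpelisib is interrupted and the table lists "Prednisone 50mg a day over 10 days (with pneumocystis prophylaxis and PPI". At grade 4, alpelisib is stopped permanently.

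On care outside the trial, Section 3.5 says of drug reactions associated with eosinophils that "drug interruption/discontinuation and systemic steroids are current reactive management strategies". It gives no grade threshold. The same section reports 17 patients with grade 2/3 alpelisib rash in an earlier trial at the institution, whose rash did not return once corticosteroids were stopped and alpelisib was resumed at the initial dose.

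**The concern.** Milligrams of steroid and counts of dose changes are clinician actions taken in response to rash, not direct measures of rash. A comparison with historical controls isolates benralizumab only if both groups were treated in the same way at each rash grade. The documents describe the trial's approach. They do not identify the controls for these outcomes or say how their rash was managed, and they plan no restriction, stratification or adjustment for it.

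If controls with grade 2 rash often received systemic steroids or had alpelisib held, and trial patients with the same rash did not, the trial arm would show less steroid and fewer dose changes even if benralizumab prevented no rash at all. At stake is a steroid-sparing or dose-preserving claim that the data could not support.

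**Working it through.** **The plan's own figure.** Section 14 states: "Sample sizes of 57 patients achieves an 80% power to detect a difference based on a two sample proportions test". Section 1.0 gives the inputs: "The proportion in the experimental group is assumed to be 0.66 under the null" "hypothesis and 0.88 under the alternative hypothesis". Alpha is not stated; I assume 0.05 two-sided. With the pooled two-sample formula and mean proportion 0.77:

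n = [1.960·√(2·0.77·0.23) + 0.842·√(0.66·0.34 + 0.88·0.12)]² / 0.22² = (1.166 + 0.483)² / 0.0484 ≈ 56.2, so 57 per group.

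Then 57 × 1.1 = 62.7, so 63. Both figures reproduce, but they concern the primary endpoint. No sample size, power or control value is given for steroid dose or dose changes. The calculation does suggest a working control-group size, because a two-sample formula implies 57 controls.

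**Inputs for the illustration**
- Grade 2 or higher rash: 34% in both groups (Section 14), so benralizumab has no effect.
- Grade 3 share g: not given for alpelisib in the documents; assumed 5–20%. Grade 2 is then 0.34 − g. Grade 4 is ignored.
- Share s of grade 2 controls given systemic steroids: not given; varied from 0 to 100%.
- Trial patients receive steroids at grade 3 only, as Table 2 lists. Controls receive them at grade 3, plus a share s at grade 2.
- Dose per treated patient: 50 mg × 10 days = 500 mg, taking the Table 2 course as a constant daily dose. Because every treated patient gets the same amount, the rank test does not depend on this value.
- 57 trial patients and 57 controls; steroid given for other reasons is ignored.

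**Formulas.** Share on steroids: trial g; controls g + (0.34 − g)·s. Spurious gap: (0.34 − g)·s. With g = 0.10 and s = 0.5 the gap is 0.24 × 0.5 = 0.12. Mean dose is 500 × 0.10 = 50 mg in the trial and 500 × 0.22 = 110 mg in controls.

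**Result.** Percentage of simulated trials (4,000 per cell, Wilcoxon, two-sided 0.05) with a significant steroid reduction in the trial arm despite no drug effect:

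| Grade 3 share | s = 0 | s = 25% | s = 50% | s = 75% | s = 100% |
|---|---|---|---|---|---|
| 5% | 2.4 | 28 | 69 | 92 | 99 |
| 10% | 2.7 | 15 | 42 | 70 | 89 |
| 15% | 2.3 | 9 | 24 | 45 | 67 |
| 20% | 2.8 | 7 | 14 | 25 | 39 |

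The Monte Carlo standard error is at most √(0.25/4000) = 0.8 points. Since each patient's dose is either 0 or 500 mg, the probabilities can also be summed exactly over two binomial distributions; that agrees within 1.5 points. In the s = 0 column controls follow the trial's rule, and the rate is the nominal 2.5% in one direction. The excess therefore comes from the management difference alone. With 100 controls and g = 10%, the figures at s = 50% and 100% are 48% and 94%.

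**Dose changes.** These figures do not carry over. RDI and the Poisson count take in every cause of dose change. Table 3 interrupts alpelisib for grade 3 hyperglycemia, which Section 15 reports in 33% of patients; Tables 7 and 8 add diarrhea and other toxicities. The same mechanism acts on the rash-related part only. The documents do not allow that part to be sized.

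**The case against.** The strongest reply is that no passage shows control care to have differed. Section 3.5 speaks of eosinophil-associated drug reactions in general, and its strategy is the one that Table 2 lists at grade 3, so the controls could have been managed by the same rule. The 17 earlier patients are not split by grade. A reader might infer that controls did receive steroids and interruptions at grade 2; the documents support only that they may have.

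A reader might also infer that Table 2 fixes trial care, so that each trial patient with grade 2 rash contributes no steroid and no dose change. It does not go that far. The column is a recommendation, nothing forbids a steroid at grade 2, and Section 11 refers active rash to dermatology for management. Departures from the table would shrink the gap.

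Nor is a bias in favour of benralizumab certain. It is the likelier direction given Section 3.5, but controls treated less intensively than Table 2 lists at grade 3 would push the comparison the other way.

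Finally, these are secondary outcomes without a power calculation, in a trial that Section 14 calls exploratory and whose endpoints are first summarised descriptively. The unidentified control source affects every historical comparison, not just these two.

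All of this stands, and it limits what can be said about size and direction. It does not supply what is missing: with control care unknown and no adjustment planned, neither test can tell management from drug.

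**Conclusion.** The point holds in conditional form. If control rash was managed differently from Table 2 at the same grade, the planned comparisons can show a difference with no benralizumab effect, and nothing in Section 14 would reveal it. Steroid dose is the more exposed outcome; dose changes are exposed to a lesser, unquantified degree.

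For steroid dose, false significance is nominal if no grade 2 control received steroids. It is about 7–28% if a quarter did, 14–69% if half did and 39–99% if all did. The ranges span grade 3 shares of 20% down to 5%. They rest on the assumed grade 3 share, control practice, 57 controls and equal dose per treated patient, and they illustrate the mechanism rather than estimate the bias in this trial. The primary endpoint's sample size is not affected. Correcting this is worthwhile mainly because it is cheap.

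**What to change.** In Section 14:

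1. Name the historical control source for steroid dose and for dose modification, and report its steroid and dose-modification practice by rash grade. Complete the Wilcoxon sentence by naming the second group.
2. Limit the Wilcoxon and Poisson comparisons to controls managed under grade-specific rash rules comparable to Table 2.
3. If no such cohort exists, report both outcomes for the trial arm only, descriptively by worst rash grade with 95% confidence intervals, and make no steroid-sparing or dose-preserving claim against historical controls.

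The cost is a change of analysis wording plus the work of characterising the control cohort. The downside is that two secondary p-values may be lost. No change to Table 2 or to any clinical rule is proposed.

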### Hyperglycemia

Table 3. Dose modification and management for hyperglycemia

Fasting Plasma Glucose (FPG)/Blood Glucose Values	Recommendation
Grade 1  FPG > ULN-160 mg/dL or > ULN-8.9 mmol/L	No dose adjustment required.  Initiate metformin 500 mg AC QD (titrate up by 500 mg QD weekly as needed and tolerated to max 2000 mg per day)
Grade 2  FPG > 160-250 mg/dL or > 8.9-13.9 mmol/L	No dose adjustment required.  Initiate/maximize metformin and add secondary non-insulin agent  If persistent Grade 2 hyperglycemia, add another secondary non-insulin agent or a tertiary non-insulin agent  If FPG does not decrease to $\leq$ 160 mg/dL or 8.9 mmol/L within 21 days under appropriate antidiabetic treatment, reduce dose by 1 dose level and follow FPG value specific recommendations.
Grade 3  > 250-500 mg/dL or > 13.9-27.8 mmol/L	Interrupt alpelisib.  Administer intravenous hydration and consider appropriate treatment (e.g., intervention for electrolyte/ketoacidosis/hyperosmolar disturbances which may include short-term insulin).  Initiate/maximize metformin, add secondary non-insulin agent plus additional secondary non-insulin agent or tertiary non-insulin agent.  If FPG decreases to $\leq$ 160 mg/dL or 8.9 mmol/L within 3 to 5 days under appropriate anti-diabetic treatment, resume alpelisib without dose adjustment for first grade 3 occurrence. If second or third occurrence, resume at 1 or 2 lower dose levels, respectively.  If FPG improves to grade 2 (160-250 mg/dL or 8.9-13.9 mmol/L) after addition of secondary non-insulin agent (Table 3), follow dose modification and management for grade 2 hyperglycemia (see above).  If FPG does not decrease to $\leq$ 160 mg/dL or 8.9 mmol/L within 3 to 5 days days, initiate/maximize non-insulin antidiabetic treatment or, if needed, add insulin (Table 5).  If FPG does not decrease to $\leq$ 160 mg/dL or 8.9 mmol/L within 21 days following antidiabetic treatment, permanently discontinue alpelisib treatment.
Grade 4	Interrupt alpelisib.


> 500 mg/dL          or <math>\geq 27.8</math> mmol/L
	
Administer intravenous hydration and consider appropriate treatment (e.g., intervention for electrolyte/ketoacidosis/hyperosmolar disturbances which may include short-term insulin), re-check FPG within 24 hours and as clinically indicated.
 
Initiate/maximize metformin, add secondary non-insulin agent (Table 3) plus additional secondary non-insulin agent (Table 3) or tertiary non-insulin agent (Table 4). Add insulin (Table 5).
 
If FPG decreases to <math>\leq 500</math> mg/dL or 27.8 mmol/L, follow FPG value specific recommendations for Grade 3.
 
If FPG is remains at <math>> 500</math> mg/dL or 27.8 mmol/L after IV hydration and acute antidiabetic treatment, permanently discontinue alpelisib treatment.

---	---

Table 4. Secondary non-insulin agents for antihyperglycemia treatment

Class	Risk for weight loss	Drug and recommended dosage A	Other Considerations for Treatment A,B
DPP-4 inhibitors	No	
 
• Alogliptin 25 mg
 
• Saxagliptin 5 mg
 
• Linagliptin 5 mg
 
• Sitagliptin 100 mg
 
	
 
• Typically well tolerated
 
• Theoretical risk of acute pancreatitis
 
• Joint pain
 

Thiazolidinediones	No	
 
• Pioglitazone 45 mg
 
• Rosiglitazone 4 mg
 
	
 
• Exercise extreme caution when using in patients with or at risk for congestive heart failure and patients at risk falls/fractures
 

GLP-1 receptor agonists	Yes	
 
• Exenatide (extended release) 2 mg powder for suspension or pen
 
• Exenatide 10 <math>\mu</math>g pen
 
• Dulaglutide 1.5/0.5 mL pen
 
• Semaglutide 1 mg pen
 
• Liraglutide 18 mg/3 mL pen
 
	
 
• GI AEs are common (nausea, vomiting, diarrhea)
 
• Injection site reactions
 
• Risk of pancreatitis
 
• Risk of thyroid C-cell tumors
 

$\alpha$ -Glucosidase inhibitors	No	
 
• Acarbose 100 mg
 
	
 
• GI AEs are common
 

A. American Diabetes Association. Standards of medical care in diabetes-2019. Diabetes Care 2019;42:S1-S193;

B. Pfeiffer AF and Klein HH. The treatment of type 2 diabetes. Dtsch Arztbl Int 2014;111:69-82

Table 5. Tertiary non-insulin agents for antihyperglycemia treatment

Class	Risk for weight loss	Drug and recommended dosage A	Other Considerations for Treatment A,B
Meglitinides	No	
 
Nateglinide 60-120 mg AC
 
Repaglinide 0.5-4 mg AC
 
	Potential AEs include: 
 
Hypoglycemia
 
Weight Gain
 
Diarrhea
 
Nausea
 

Sulfonylureas	No	
 
Glimepiride 1-8 mg PO OD
 
Glipizide 5-40 mg PO (OD or split dose BID)
 
Glipizide XR 5-20 mg PO
 
Glyburide* 2.5-20 mg OD
 
Glyburide micronized* 3-12 mg OD
 
	Potential AEs include: 
 
Hypoglycemia
 
Weight Gain
 
Diarrhea
 
Nausea
 

A. American Diabetes Association. Standards of medical care in diabetes-2019. Diabetes Care 2019;42:S1-S193;

B. Pfeiffer AF and Klein HH. The treatment of type 2 diabetes. Dtsch Arztebl Int 2014;111:69-82

\*contraindicated with eGFR<30; OD, once daily; AC, before meals

Table 6. Insulin for antihyperglycemia treatment

Class	Risk for weight loss	Drug	Recommended starting dose	Other Considerations for Treatment A,B
Basal insulin	No	
 
Insulin glargine
 
Insulin detemir
 
	0.2 units per kg SC OD Increase for goal fasting FSBG < 160 mg/dL	Potential AEs include: 
 
Hypoglycemia
 
Weight Gain
 

Rapid acting insulin	No	
 
Insulin aspart
 
Insulin lispro
 
Insulin glulisine
 
	Start sliding scale AC FPG Units 70-99 0 100-149 0 150-199 2 200-249 3 250-299 4 300-349 5 350-399 6 over 400 7	Potential AEs include: 
 
Hypoglycemia
 
Weight Gain
 

A. American Diabetes Association. Standards of medical care in diabetes-2019. Diabetes Care 2019;42:S1-S193;

B. Pfeiffer AF and Klein HH. The treatment of type 2 diabetes. Dtsch Arztebl Int 2014;111:69-82

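### Table 3 tells sites both to reduce and to stop alpelisib when grade 3 hyperglycemia settles at 161–250 mg/dL, and does not say whether a held drug restarts

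*Combined protocol and SAP*

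**What the plan says.** All of this is in protocol section 10.0, Table 3 (Hyperglycemia), unless stated otherwise. FPG is fasting plasma glucose.

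- **Grade 3 row, opening (above 250 to 500 mg/dL):** "Interrupt alpelisib".
- **Grade 3 row, resuming:** if FPG falls to 160 mg/dL or below "within 3 to 5 days under appropriate anti-diabetic treatment, resume alpelisib without dose adjustment for first grade 3 occurrence". No other condition for resuming is written in the row.
- **Grade 3 row, partial improvement:** if FPG improves to the grade 2 range (160–250 mg/dL) after a secondary agent is added, "follow dose modification and management for grade 2 hyperglycemia (see above").
- **Grade 2 row:** the dose is left unchanged at first. If FPG has not come down to 160 mg/dL or below "within 21 days under appropriate antidiabetic treatment, reduce dose by 1 dose level and follow FPG value specific recommendations".
- **Grade 3 row, last clause:** if FPG has not come down to 160 mg/dL or below "within 21 days following antidiabetic treatment, permanently discontinue alpelisib treatment".
- **Grade 4 row:** a patient who falls to 500 mg/dL or below moves to the Grade 3 rules. For drug choice the row points to "or tertiary non-insulin agent (Table 4). Add insulin (Table 5"), but the insulin list is headed "Table 6. Insulin for antihyperglycemia treatment".
- **Section 12.0:** more than two consecutive weeks of treatment delay due to toxicity is a criterion for removal from study.
- **Section 13.2:** 4W-RDI, a secondary endpoint, is the cumulative alpelisib dose in the first four weeks divided by the standard dose.

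**The concern.** Consider a patient with a first grade 3 value who improves to 200 mg/dL on a secondary agent and stays there. At 21 days two clauses apply, with the same threshold and the same time limit. One keeps the patient on alpelisib at a lower dose and the other ends alpelisib for good. Nothing in the protocol says which governs.

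There is also a gap earlier in the same patient's course. The drug has been interrupted, and the one stated route back to dosing needs FPG of 160 mg/dL or below. The patient is instead sent to a row that starts from an unchanged dose and later reduces it, so it presupposes a patient who is taking the drug. Whether and when dosing restarts is not stated.

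The stakes are patient management and consistency across the three participating centers: whether a patient with metastatic cancer continues a treatment, and whether identical patients are handled alike. Hyperglycemia is also the leading adverse event behind alpelisib discontinuation in section 3.3 (18 patients, 6.3%, against 9 patients, 3.2%, for rash). An unclear restart rule feeds into 4W-RDI as well.

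**Working it through.** The plan gives no figure to reproduce here. The check is to apply the clauses as written, then gauge scale.

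**Step 1. Which clauses apply at 21 days to a patient who entered at grade 3?**

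| FPG at 21 days | Grade 2 row, by referral | Last clause of Grade 3 row |
|---|---|---|
| 160 mg/dL or below | reduction not triggered | stop not triggered |
| 161–250 mg/dL | reduce one level | stop permanently |
| above 250 mg/dL | referral does not apply | stop permanently |

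The clash is confined to 161–250 mg/dL. It arises because the stop clause is triggered by failure to reach 160 mg/dL, not by failure to reach 250 mg/dL, so its wording still covers patients already referred to the Grade 2 row.

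**Step 2. Days 3–5 of the hold, FPG 161–250 mg/dL.** The resume clause is not met. The referral clause leads to an unchanged dose. A further Grade 3 clause, for FPG not at 160 mg/dL or below by days 3–5, intensifies antidiabetic treatment and does not mention alpelisib. No clause says restart and none says keep holding.

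**Step 3. Interaction with section 12.0.** Assume grade 3 onset, hold and antidiabetic treatment all start on day 15, and that a hold counts as a delay. Day 15 is the section 15.0 median for first hyperglycemia of grade 2 or higher; no grade 3 median is given. Fourteen days of hold run from day 15 to day 28, so the two-week limit is passed on day 29. The 21-day decision falls on day 15 + 21 = day 36. On the continued-hold branch the removal criterion therefore comes first.

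**Step 4. Number of patients.** Section 15.0 gives 33% grade 3 and 3.9% grade 4.

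- Grade 3: 0.33 × 63 = 20.8, about 21 patients.
- Grade 3 or 4: (0.33 + 0.039) × 63 = 23.2, about 23 patients.

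These rates are not limited to four weeks, and the share who remain at 161–250 mg/dL is not given. The counts are upper bounds on those affected if the rates carry over to this trial.

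**Step 5. 4W-RDI.** Take the denominator as 28 days × 300 mg, with 300 mg daily before the hold and on resumption, so that 4W-RDI = days dosed / 28. With onset on day 15 (14 days dosed before the hold):

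- held to day 28: 14/28 = 50.0%;
- resumed after a 4-day hold (dosed days 19–28): (14 + 10)/28 = 24/28 = 85.7%;
- resumed after a 5-day hold (dosed days 20–28): (14 + 9)/28 = 23/28 = 82.1%.

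Varying onset from day 6 to day 22, holding to day 28 gives 5/28 = 17.9% to 21/28 = 75.0%. Resuming after five days gives 23/28 = 82.1% throughout.

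**Step 6. Can the 21-day clash move 4W-RDI?** On the day-15 example, no: day 36 lies outside the 28-day window. Onset on day 8 already puts the decision on day 29. Only onset by day 7 brings it to day 28 or earlier, with a few doses at stake.

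**Step 7. Table pointers.** Table 3 cites Table 3 for secondary agents, Table 4 for tertiary agents and Table 5 for insulin. The lists are in Tables 4, 5 and 6. The Table 5 reached from the insulin instruction lists meglitinides and sulfonylureas, which are non-insulin agents.

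**The case against.** The best defense is that the referral to the Grade 2 row takes the patient out of the remaining Grade 3 clauses, so the stop clause is meant only for patients who never reach grade 2. That is a sensible reading, but the text does not state it and the stop clause's 160 mg/dL threshold does not fit it. It shows how the conflict might be resolved, not that it is absent. Likewise, the dose rules are headed as recommendations and guidelines, and section 10.0 leaves continuation to the treating clinician's judgment of progression and toxicity. That softens the consequence without supplying an answer.

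Several stronger readings should be set aside.

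- **Opposite orders at days 3–5.** A reader might infer that the table orders both resumption and a continued hold. It does neither at 161–250 mg/dL; this is silence on restarting.
- **Certain divergence.** The documents show that sites may differ, not that they will.
- **A further conflict with Table 1 at the third occurrence.** One could count the two lower levels from an already reduced 250 mg and fall below the Table 1 floor ("If further dose reduction below 200 mg once daily is required, discontinue alpelisib"). But no change, one level and two levels at successive occurrences fit Table 1's 300, 250 and 200 mg, and the other count would defeat the instruction to resume.
- **Bias in the primary endpoint.** Rash grade at four weeks is not defined by Table 3, section 3.4 puts the median onset of grade 3–4 rash at 13 days, before the day-15 hold in the example, and no effect on the rash rate can be derived from the documents.

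The pointer errors are clerical, and the captions would alert most readers. They still need correcting, because one sits in the instruction for FPG above 500 mg/dL.

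**Conclusion.** The point holds for a defined group: patients with grade 3 hyperglycemia (or grade 4 falling into the Grade 3 rules) who improve to 161–250 mg/dL after a secondary agent. If still above 160 mg/dL at 21 days, they meet two incompatible written instructions with no precedence between them. Before that, the restart of held alpelisib is unaddressed, and a continued hold would run into the section 12.0 removal criterion before the 21-day rule is reached.

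The ceiling is about 21 of 63 patients, or about 23 with grade 4; the true number is unknown. The restart gap could shift an affected patient's 4W-RDI from 50% to 82–86%, given onset on day 15 and dosing at 300 mg. The 21-day clash matters for patient management and site consistency, and except with very early onset it does not bear on 4W-RDI. No consequence for the primary endpoint is shown. The off-by-one table pointers are confirmed.

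**What to change.** The sponsor's clinical team should amend section 10.0 and section 12.0 together so that:

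1. a patient who entered at grade 3 and is at 161–250 mg/dL has one explicit instruction on whether and when held alpelisib restarts;
2. the same patient has one instruction at 21 days, with the Grade 2 clause and the last Grade 3 clause reconciled or their order of precedence stated;
3. both are consistent with the removal criterion of more than two consecutive weeks of delay, including whether a hold for hyperglycemia counts as such a delay;
4. the pointers in the Grade 3 and Grade 4 rows lead to Table 4 for secondary agents, Table 5 for tertiary agents and Table 6 for insulin.

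Which rule should apply is a clinical decision for the sponsor, and no view on it is given here. The cost is a wording amendment, circulated to all three centers, with no added patients, visits or procedures.
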